7.1.5.2. Incomplete Dates

If the onset date of the AE is incomplete and the AE stop date is not prior to the first dosing date of study drug, then the month and year (or year alone if month is not recorded) of onset date determine whether an AE is treatment emergent. For first dosing date and last dosing date defined for the Induction Studies (Cohort A Induction Study and Cohort B Induction Study), Maintenance Study and Overall, please refer to Section 3.8.1. The event is considered treatment emergent if both of the following 2 criteria are met:

Induction Studies (Cohort A Induction Study and Cohort B Induction Study)

- The AE onset date is the same as or after the month and year (or year) of the first dosing date of study drug, and
- The AE onset date is the same as or before the month and year (or year) of the date corresponding to
 - 30 days after the last dosing date of Induction Study, for subjects who did not take any treatment from Maintenance, or
 - the day before the first dosing date of Maintenance Study, for subjects who took any study treatment in Maintenance Study

Maintenance Study

- The AE onset date is the same as or after the month and year (or year) of the first dosing date of Maintenance Study and
- The AE onset date is the same as or before the month and year (or year) of the date corresponding to 30 days after last dosing date of Maintenance Study

Overall (Induction and Maintenance)

- The AE onset date is the same as or after the month and year (or year) of the first dosing date of study drug, and
- The AE onset date is the same as or before the month and year (or year) of the date corresponding to 30 days after last dosing date of either Induction Study or Maintenance Study, whichever is later

An AE with completely missing onset and stop dates, or with the onset date missing and a stop date later than the first dosing date of study drug, will be considered to be treatment emergent. In addition, an AE with the onset date missing and an incomplete stop date with the same or later month and year (or year alone if month is not recorded) as the first dosing date of study drug will be considered treatment emergent.

7.1.6. Summaries of Adverse Events and Deaths

Treatment-emergent AEs will be summarized based on the Safety Analysis Set for Cohort A Induction Study, Cohort B Induction Study, Cohort A and B Induction Studies Combined, Maintenance Study, and Overall separately.

No formal statistical testing is planned.

7.1.6.1. Summaries of AE incidence

The number and percentage of subjects who experienced at least 1 TEAE will be provided and summarized by SOC, HLT, PT, and treatment group. For other AEs described below, summaries will be provided by SOC, PT, and treatment group:

- TEAEs of Grade 3 or higher (by maximum severity)
- TEAEs of Grade 2 or higher (by maximum severity)
- All TE treatment-related AEs
- TE treatment-related AEs of Grade 3 or higher (by maximum severity)
- TE treatment-related AEs of Grade 2 or higher (by maximum severity)
- All TE SAEs
- All TE treatment-related SAEs
- All TEAEs leading to premature discontinuation of study drug
- All TEAEs leading to premature discontinuation of study
- All TE SAEs leading to death (ie, outcome of death)
- All TEAEs leading to temporary dose interruption of study drug

A brief, high-level summary of AEs described above will be provided by treatment group presenting the number and percentage of subjects who experienced the above AEs. All deaths observed in the study will be also included in this summary.

Multiple events will be counted only once per subject in each summary. Adverse events will be summarized and listed first in alphabetic order of SOC and HLT within each SOC (if applicable), and then by PT in descending order of total frequency within each SOC. For summaries by severity grade, the most severe grade will be used for those AEs that occurred more than once in an individual subject during the study.

In addition, the following tables will be generated and summarized by PT only, in descending order of total frequency:

- TEAEs
- TEAEs of Grade 3 or higher
- TEAEs of Grade 2 or higher
- TE SAEs
- TE treatment-related AEs
- TE treatment-related SAEs
- TEAEs leading to premature discontinuation of study drug

Data listings will be provided for the following:

- All AEs, indicating whether the event is treatment emergent
- All AEs of Grade 3 or higher
- All AEs of Grade 2 or higher
- SAEs
- Deaths
- All AEs leading to death (ie, outcome of death)
- AEs leading to premature discontinuation of study drug
- AEs leading to premature discontinuation of study
- AEs leading to dose temporary interruption of study drug

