**Table 3-1. Re-randomization for Maintenance Study**

Treatment Assignment Induction Studies Cohorts A and B	Maintenance Study Re-randomization:
Treatment 1, filgotinib 200 mg	Treatment 1, 200 mg
	Treatment 3, Placebo
Treatment 2, filgotinib 100 mg	Treatment 2, 100 mg
	Treatment 3, Placebo
Treatment 3, Placebo	Continue Treatment 3, Placebo

Note: Subjects receiving Treatment 1 or 2 in the Induction study will be randomized in a 2:1 manner to either continue on the assigned filgotinib regimen or to placebo for the duration of the Maintenance study.

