### 3.6. Disease Worsening Criteria

Subjects meeting the following disease worsening criteria evaluated starting at Week 11 must be discontinued from blinded treatment and will be offered the option to receive open-label filgotinib by entering into the separate LTE study (GS-US-418-3899).

- Disease worsening starting at 11 weeks of therapy is based on the following criteria: partial MCS score (all components of MCS except for endoscopic subscore) increase of  $\geq 3$  points to at least 5 points from the Week 10 value on two consecutive visits, or an increase to 9 points on two consecutive visits if the Week 10 value is  $> 6$ .
  - The disease worsening visits may include unscheduled visits (eg, a study visit followed by an unscheduled visit, or 2 sequential unscheduled visits anytime from Week 11 onward).
- Disease worsening to the extent that the subject clinically requires medications prohibited by the study (at investigator discretion, with discussion with medical monitor if feasible); these subjects do not qualify for the LTE study.

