### **Overall (Induction and Maintenance)**

All safety data collected on or after the first dose of study drug administration for the entire study (Day 1) up to 30 days after permanent discontinuation of study drug will be summarized by treatment group according to the study drug received.

All data collected during the course of study will be included in data listings.

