### **Overall (Induction and Maintenance)**

- Any AEs with an onset date of on or after the study drug start date for the entire study (Day 1) and up to 30 days after permanent discontinuation of study drug.
- Any AEs leading to premature discontinuation of study drug.

Summaries (number and percentage of subjects) of TEAEs by SOC and PT will be provided by treatment group. TEAEs will also be summarized by relationship to study drug and severity. In addition, TEAEs leading to premature discontinuation of study drug will be summarized and listed.

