### 8.9.2. Maintenance Study

Assuming an induction response rate (ie, proportion of subjects achieving EBS remission or MCS response at Week 10) of 55% among subjects receiving filgotinib 200 mg or filgotinib 100 mg treatment, approximately 285 subjects from each filgotinib dose group from Cohorts A and B Induction Studies combined would be eligible to be re-randomized into the Maintenance Study.

The sample size was chosen to ensure that a clinically meaningful difference in EBS remission rate at Week 58 could be detected when comparing each filgotinib dose group (200 mg or 100 mg) to placebo in the Maintenance Study. A sample size of 95 subjects in the placebo group and 190 subjects in the filgotinib group at the same dose level as the induction dose will provide more than 85% power for each filgotinib dose group comparison to placebo at a 2-sided 0.025 significance level to detect a treatment difference in maintenance EBS remission rate of 20% (40% on filgotinib and 20% on placebo).

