3.2. Subject Grouping

For analyses based on the All Randomized Analysis Sets and FAS, subjects will be grouped according to the treatment to which they were randomized. For analyses based on the Safety Analysis Sets, PP Analysis Sets, and Biomarker Analysis Set, subjects will be grouped according to actual treatment received. The actual treatment received will differ from the randomized treatment only when their actual treatment differs from randomized treatment for the entire treatment duration.

For the PK Analysis Sets, subjects will be grouped according to the actual treatment they received.

For the summary of AEs and laboratory abnormalities using the Overall Safety Analysis Set, subjects will be grouped according to the actual treatment received across Induction and Maintenance studies, if applicable.

In general, all data will be summarized by treatment group for:

- Cohort A Induction Study
- Cohort B Induction Study
- Cohort A and B Induction Studies combined (not applicable to efficacy analysis)
- Maintenance Study

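### Overall adverse-event percentages compare groups with unequal time at risk, in columns the SAP does not name and with no Overall exposure summary (minor)

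*SAP*

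**What the plan says.** Protocol 8.6.2 sets the metric: "Summaries (number and percentage of subjects) of TEAEs by SOC and PT will be provided by treatment group". SAP 7.1.6.1 repeats it ("The number and percentage of subjects who experienced at least 1 TEAE will be provided and summarized by SOC, HLT, PT, and treatment group"), and SAP 7.1.7 applies it to infections, herpes zoster, malignancy, gastrointestinal perforation and thromboembolism. SAP 7.1.6 asks for these tables for each cohort, both cohorts combined, Maintenance and Overall, without formal testing. Neither document plans a patient-time denominator or a time-to-event safety summary.

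Under SAP 7.1.5.1 the Overall window is a single span from the first dose to 30 days after the later of the two last-dose dates. Week 10 non-responders are not re-randomized. Filgotinib responders "will be randomized in a 2:1 manner to either continue on the assigned filgotinib regimen or to placebo" (Protocol Table 3-1). In Maintenance, subjects who meet the worsening criteria "must be discontinued from blinded treatment and will be offered the option to receive open-label filgotinib" (Protocol 3.6).

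On Overall grouping, Protocol 8.6 says the data "will be summarized by treatment group according to the study drug received". SAP 3.2 says that "subjects will be grouped according to the actual treatment received across Induction and Maintenance studies, if applicable". Neither lists the columns. SAP 4.2 summarizes exposure for Cohort A, Cohort B, the cohorts combined and Maintenance, but not for Overall.

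**The concern.** A percentage of subjects with an event is a fair comparison when groups are followed for about the same time. In Overall they are not, even if nobody stops early. A non-responder contributes about 11 weeks plus the 30-day tail, and a responder about 58 weeks plus the tail. A column's mean time at risk therefore depends on its share of responders and on where filgotinib-to-placebo subjects are placed.

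The tables are descriptive, but readers will compare columns for uncommon events such as zoster or thromboembolism. From n (%) alone they cannot separate a difference in rate from a difference in follow-up. For Overall there is no exposure table to turn to.

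**Working it through.** **Group sizes.** Each dose has 2 × 260 = 520 randomized subjects and placebo has 2 × 130 = 260. At the assumed 55% response, 0.55 × 520 = 286. This reproduces the plan's figure in Protocol 8.9.2 ("approximately 285 subjects from each filgotinib dose group from Cohorts A and B Induction Studies combined would be eligible to be re-randomized"). A 2:1 split gives 190.7 continuing and 95.3 switching to placebo per dose (plan: 190 and 95), so 190.7 switchers over both doses. Filgotinib non-responders number 520 − 286 = 234 per dose.

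**Assumptions not in the documents.** Every group has a constant event rate of 5 per 100 patient-years, placebo response q is 20%, 35% or 50%, and nobody stops early in Overall.

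**Time at risk, with the SAP's one-span window and 30-day tail (4.3 weeks).** Non-responder: 11 + 4.3 = 15.3 weeks. Responder: 11 + 47 + 4.3 = 62.3 weeks.

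**Risk of at least one event**, 1 − exp(−0.05 × weeks / 52.18): 1.454% for a non-responder and 5.794% for a responder.

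**Column risks.**
- Started on a filgotinib dose: (234 × 1.454 + 286 × 5.794) / 520 = 3.84%.
- Filgotinib only: (234 × 1.454 + 190.7 × 5.794) / 424.7 = 3.40%.
- Placebo only: (1 − q) × 1.454 + q × 5.794 = 2.32%, 2.97%, 3.62%.
- Ever on placebo: (260 × placebo-only risk + 190.7 × 5.794) / 450.7 = 3.79%, 4.17%, 4.54%.

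**Crude filgotinib/placebo risk ratio; the true rate ratio is 1.00.**

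| Overall grouping | q = 20% | q = 35% | q = 50% |
|---|---|---|---|
| Sequence: filgotinib only vs placebo only | 1.47 | 1.14 | 0.94 |
| Any exposure: ever on dose vs ever on placebo | 1.01 | 0.92 | 0.85 |
| Initial arm | 1.65 | 1.29 | 1.06 |

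In the any-exposure row, a switcher's whole span counts in both columns, because the SAP window does not divide events by period.

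**Chance variation.** The 95% factor is exp(1.96 × SE of log ratio), with SE² = (1 − p₁)/(n₁p₁) + (1 − p₂)/(n₂p₂). For the initial arm (520 vs 260) it is 2.45 to 2.14 as q rises from 20% to 50%, and 1.56 to 1.45 at 20 per 100 patient-years. At that higher rate and q = 20%, the two risks are 14.24% and 8.80%, a ratio of 1.62, slightly above the factor of 1.56. At 5 per 100 patient-years, every ratio in that row is inside its factor.

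**Maintenance.** Stopping is exponential over 47 weeks, time at risk runs to last dose + 30 days, and the groups are 190 and 95. Stopping rates are assumptions.
- Equal stopping: 1.00.
- 20% vs 50% (filgotinib vs placebo): 46.4 vs 38.2 mean weeks, 4.34% vs 3.58%, ratio 1.21. The chance factor is 3.45. It is 1.83 at 20 per 100 patient-years (ratio 1.21) and 1.27 at 100 (ratio 1.17).
- 30% vs 70%: 4.10% vs 2.97%, ratio 1.38.

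Under these assumptions, dividing subjects with an event by patient-years to first event or end of follow-up gives a ratio of 1.00 in every case.

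**The case against.** The SAP's metric agrees with the protocol, so there is no contradiction or calculation error. The randomized comparisons, Induction and Maintenance, are tabulated separately with their own exposure summaries, and disposition tables give reasons for stopping. Overall is supplementary. The revision log in SAP 12 suggests that limiting it to adverse events and laboratory abnormalities was deliberate. It mixes randomized groups with responder selection, which patient-time does not undo. An integrated safety SAP is mentioned there but was not supplied. All of this stands and keeps the priority low. It does not give the Overall percentages a time base or name their columns.

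Three stronger readings are tempting and not supported:

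- A reader might infer that SAP 3.2 puts switchers in their initial arm, because actual treatment departs from randomized treatment "only when their actual treatment differs from randomized treatment for the entire treatment duration". That rule concerns subjects who were given a drug other than the one assigned. Switchers were re-randomized to placebo, so it does not address them. The separate Overall sentence fits sequence better, as does the SAP 5.1 display by induction and maintenance dose.
- A reader might infer that the Maintenance tables mislead. Exposure by treatment group is tabulated up to 47 weeks in SAP 4.2.1, and the distortion is nil with equal stopping and otherwise below chance in the 20% vs 50% scenario.
- A reader might take the gap between switchers and placebo-only subjects (5.794 / 2.32 = 2.50 at q = 20%) as the size of the problem. That is not a filgotinib/placebo contrast: every switcher is a responder followed into Maintenance.

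**Conclusion.** The point holds as a minor one, mainly for Overall. With equal true rates, crude Overall ratios can run from 1.47 to 0.94 under the most natural grouping, and from 1.65 down to 0.85 across the three groupings considered. Both size and direction depend on columns the SAP does not name. These figures rest on assumed event and placebo response rates, on planned group sizes and on no early stopping; the documents give no values for the first two. Most of the distortion is smaller than chance at these sample sizes, so this is a matter of interpretability and not a demonstrated bias in a safety conclusion. The missing column names alone would be no more than absent detail. What justifies a change is that a better summary can be made from dates already collected.

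**What to change.** Keep n (%). In SAP 7.1.6 and 7.1.7, for Overall and for consistency Maintenance, add subjects with an event per 100 patient-years at risk with 95% CI. Do this for any TEAE, SAEs, TEAEs leading to discontinuation of study drug and each adverse event of interest. End time at risk at the earlier of the first event or last dose + 30 days. State how the 30-day tail is counted for subjects who enter the extension study, since Protocol 6.5 exempts them from the post-treatment visit. In SAP 3.2, name the Overall columns by treatment sequence. Add Overall to the exposure summary in SAP 4.2.1.

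The cost is a few descriptive tables and one or two sentences, with no protocol change or new data. The tables may overlap with the integrated safety SAP, which cannot be checked here. A footnote should say that the rates assume a constant hazard and do not remove informative stopping or responder selection.

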7.1.7. Adverse Events of Interest

Adverse events of interest (AEI) include infections, gastrointestinal perforations, herpes zoster, malignancies (excluding non-melanoma skin cancers), non-melanoma skin cancers, and thromboembolic events. Summaries of the following treatment-emergent AEs will be produced to enhance the analysis of safety data.

- Events of infections, presented in the following subcategories:
 - AEs of infections, utilizing all AEs in the MedDRA Infections and Infestations SOC
 - AEs of serious infections, using all AEs in the MedDRA Infections and Infestations SOC that are classified as SAEs
 - AEs of herpes zoster, utilizing a MedDRA search term (MST) list developed by Gilead
 - AEs of opportunistic infections (OIs), using a MST list developed by Gilead
- AEs of malignancies, excluding non-melanoma skin cancers, utilizing a MST list developed by Gilead
- AEs of non-melanoma skin cancers, utilizing a MST list developed by Gilead
- AEs of gastrointestinal perforation, utilizing a MST list developed by Gilead
- AEs of thromboembolism, presented in the following subcategories:
 - AEs of venous thrombosis, utilizing a MST list developed by Gilead
 - AEs of pulmonary embolism, utilizing a MST list developed by Gilead
 - AEs of arterial thrombosis, utilizing the embolic and thrombotic events, arterial Standardised MedDRA Queries (SMQ)
 - AEs of cerebrovascular events, utilizing the ischaemic central nervous system vascular conditions SMQ

The number and percentage of subjects with a reported event will be summarized for each treatment group by PT for each AEI category. Data listings for AEs will also be provided.

7.1.8. Additional Analysis of Adverse Events

TEAE and SAE for the following subgroups of subjects will be summarized by SOC and PT for Cohort A Induction Study, Cohort B Induction Study, Cohort A and B Induction Studies Combined, Maintenance Study, and Overall separately:

- Age group (< 65 years, ≥ 65 years; on the date of first dose of the study drug)
- Sex at birth (female, male)
- Race (Asian, Black or African American, White, Other)
- Geographic region (US, non-US)
- Prior TNF α antagonist failure (yes, no) (not applicable for Cohort A Induction Study)
- Prior vedolizumab failure (yes, no) (not applicable for Cohort A Induction Study)
- Prior dual refractory (TNF α antagonist and vedolizumab) (yes, no) (not applicable for Cohort A Induction Study)
- Concomitant use of systemic corticosteroid and immunomodulator at Day 1 (or re-baseline for Maintenance Study), including
 - Systemic corticosteroid only
 - Immunomodulator only
 - Both systemic corticosteroid and immunomodulator
 - Neither systemic corticosteroid nor immunomodulator

7.2. Laboratory Evaluations

Laboratory data collected during the study will be analyzed and summarized using both quantitative and qualitative methods. Summaries of laboratory data will be provided for the Safety Analysis Set for Cohort A Induction Study, Cohort B Induction Study, Cohort A and B Induction Studies Combined, Maintenance Study, and Overall (treatment-emergent laboratory abnormalities tables only for Overall) separately and will include data collected as specified below:

Induction Studies (Cohort A Induction Study and Cohort B Induction Study)

- No later than 30 days after the last dosing date of Induction Study, for subjects who did not take any study treatment from Maintenance Study, or
- On or before the first dosing date of Maintenance Study, for subjects who took any study treatment in Maintenance Study

Maintenance Study

- No later than 30 days after the last dosing date of Maintenance Study

Overall (Induction and Maintenance)

- No later than 30 days after the last dosing date of Induction or Maintenance Study, whichever is later

The analysis will be based on values reported in conventional units. When values are below the LOQ, they will be listed as such, and the closest imputed value will be used for the purpose of calculating summary statistics as specified in Section 3.7. Test results for hemolyzed samples will not be included in the analysis, but they will be listed in by-subject laboratory listings.

A by-subject listing for laboratory test results will be provided by subject ID number and time point in chronological order for hematology, serum chemistry, urinalysis, lipid profile, and serum immunoglobulin separately. Values falling outside of the relevant reference range and/or having a severity grade of 1 or higher on the CTCAE severity grade will be flagged in the data listings, as appropriate.

No formal statistical testing is planned.

7.2.1. Summaries of Numeric Laboratory Results

Descriptive statistics will be provided by treatment group for each laboratory test specified in the study protocol within hematology and chemistry panels including creatinine clearance, and also laboratory tests from lipids panel including total cholesterol, LDL, HDL, triglycerides, non-HDL cholesterol (total cholesterol minus HDL cholesterol), LDL/HDL ratio, and IgA, IgM, IgG, and total Ig, as follows for each Induction Study and Cohort A and B Induction Studies Combined:

- Baseline values
- Values at each postbaseline time point
- Change from baseline at each postbaseline time point

In addition, descriptive statistics for the laboratory tests described from above will be provided by treatment group for the Maintenance Study:

- Re-baseline values
- Values at each postbaseline time point after re-baseline
- Change from re-baseline at each postbaseline time point after re-baseline

A baseline laboratory value will be defined as the last measurement obtained on or prior to the date of first dose of study drug. Change from baseline to a postbaseline visit will be defined as the visit value minus the baseline value. A re-baseline laboratory value will be defined as the last measurement obtained on or prior to the date of first dose of study drug for the Maintenance study, and change from re-baseline will be defined as the visit value minus the re-baseline value. The mean, median, Q1, Q3, minimum, and maximum values will be displayed to the reported number of digits; SD values will be displayed to the reported number of digits plus 1.

Median (Q1, Q3) of the observed change from baseline (or re-baseline) values for aspartate aminotransferase (AST), alanine aminotransferase (ALT), total bilirubin, alkaline phosphatase, serum creatine, creatinine clearance, creatine phosphokinase, white blood cell count, absolute neutrophils, absolute lymphocytes, hemoglobin, platelets, total cholesterol, LDL, HDL, total Ig, IgG, IgA and IgM, will be plotted using a line plot by treatment group and visit.

In the case of multiple values in an analysis window, data will be selected for analysis as described in Section 3.8.3.

